### **6.2.11. Discontinuation From Study Treatment**

Subjects discontinued from study treatment without documented (by imaging) PD, withdrawal of consent, death or loss to follow-up should continue tumor evaluation at 6-week intervals up to the first 24 weeks after randomization, then every 12 weeks ( $\pm 7$  days) until disease progression, start of new anticancer therapy, death, withdrawal of consent, loss to follow-up, or study closure.

### **6.2.12. Subjects Deriving Clinical Benefit**

Subjects receiving clinical benefit (SD or better) from study treatment at the time of closure of the main study may be offered the opportunity to continue study treatment in an open label extension phase (see Section 6.5).

## **6.3. Follow-up Survival**

After discontinuation from study treatment, follow-up information for survival will be obtained per telephone approximately every 3 months for a minimum of 13 months.

## **6.4. Protocol Deviations**

The investigator should conduct the study in compliance with the protocol agreed to by Sponsor and, if required, by the regulatory authority(ies), and which was given approval/favorable opinion by the IRB/IEC.

A deviation to any protocol procedure or waiver to any stated criteria will not be allowed in this study except where necessary to eliminate immediate hazard(s) to the subject. Sponsor must be notified of all intended or unintended deviations to the protocol (eg, inclusion/exclusion criteria, dosing, missed study visits) on an expedited basis.

The investigator, or person designated by the investigator, should document and explain any deviation from the approved protocol.

If a subject was ineligible or received the incorrect dose of investigational treatment, and had at least one administration of investigational product, data should be collected for safety purposes.

The Investigator should notify the IEC or IRB of deviations from the protocol in accordance with local procedures.

## **6.5. Extension Phase**

Subjects receiving clinical benefit (SD or better) from study treatment at the time of closure of the main study may be offered the opportunity to continue study treatment. After database lock individual sites will be informed of subject treatment. Subjects will be provided open-label treatment in an extension phase of this study.

For subjects continuing in the extension phase, the following study procedures will be performed: physical examination, weight, vital signs, hematology, blood chemistry, HAHA levels (and PK) if HAHA is positive at the end of study treatment, blood samples for biomarkers, and AEs (see Extension Phase Schedule of Events, [Table 17.3](#)).

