### 5.1.7.1. Dose Modification of Patritumab

Patritumab is contraindicated for subjects with known hypersensitivity to either the drug substance or inactive ingredients in the drug product. In previous patritumab studies, the most common toxicities that occurred were rash, diarrhea, vomiting, nausea, fatigue, dyspnea, and skin and subcutaneous tissue disorders. Table 5.1 and Table 5.2 pertain to patritumab dose modifications.

If the initial loading dose of 18 mg/kg is not tolerated, infusion time can be extended to a maximum of 120 minutes for subjects unable to tolerate the 60 minute infusion. Patritumab/placebo is to be withheld from a subject experiencing a CTCAE Grade 3 AE, and resumed at the next regularly scheduled patritumab dosing (maintenance dose of 9 mg/kg) only after resolution of the AE to Grade 0 or 1 (or baseline grade if higher than Grade 1).

If a rash or mucositis occurs following the initial dose of patritumab 18 mg/kg, then hold the patritumab until the AE resolves to Grade 0 or 1 (or baseline grade if higher than Grade 1). If the rash or mucositis has not resolved, then hold cetuximab 250 mg/m^2 until the AE resolves to Grade 0 or 1 (or baseline grade if higher than Grade 1). If a rash or mucositis occurs on the maintenance dose of patritumab at 9 mg/kg, hold patritumab until the AE resolves to Grade 0 or 1 (or baseline grade if higher than Grade 1) and then decrease patritumab dosing to 6 mg/kg. If the AE does not resolve, hold the next dose of cetuximab until resolution to Grade 0 or 1 (or baseline grade if higher than Grade 1).

Left ventricular ejection fraction will be monitored throughout the study (see Section 9.11.1) for possible effects of patritumab treatment on cardiac function. Dose modification or suspension of patritumab treatment will be based on decreased LVEF, as outlined in Table 5.1.

For cases of ILD, refer to Section 9.3.2.

Both patritumab/placebo are to be withheld from a subject experiencing a Grade 4 AE.

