**Table 5.1: Patritumab Maintenance Dose Modification for Toxicities**

Toxicity	Withhold Criteria	Resumption Criteria	Dose Reduction Criteria	Discontinuation Criteria
All AEs a	Grade 3 or higher	Grade 0 or 1 (or baseline grade if higher than Grade 1) b	Reduce patritumab maintenance dose from 9 mg/kg to 6 mg/kg (for mucositis follow dose modification as defined above)	Failure to recover within 3 weeks

Toxicity	Withhold Criteria	Resumption Criteria	Dose Reduction Criteria	Discontinuation Criteria
Ejection fraction	Grade greater than or equal to 3, (LVEF of less than 40% or LVEF decrease of more than 20% from the baseline)	LVEF of at least 50% (or baseline) based on a repeat echocardiogram or MUGA scan performed in 3 weeks	Reduce patritumab maintenance dose from 9 mg/kg to 6 mg/kg	LVEF that does not recover within 3 weeks: Decreased $\geq$ Grade 3 <40% >20% decrease from baseline

a For elevations of aminotransferase (AST/ALT) and/or bilirubin, please see Section 4.1.4.

b Patritumab/placebo dosing may be resumed upon consultation with the Sponsor's medical monitor if the event has resolved to Grade 2.

MUGA = multigated acquisition (scan); LVEF = left ventricular ejection fraction.

Dose delays/reductions for toxicities related to patritumab are summarized in Table 5.2.

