## **9.11. Other Safety Assessments**

### **9.11.1. Echocardiograms or MUGA (LVEF Assessment)**

To monitor for possible effects of treatment on cardiac function, LVEF will be assessed at Screening, Cycle 3, and then every third subsequent cycle, the End of Treatment Visit, and as otherwise clinically indicated using either echocardiography or MUGA scanning (if MUGA is considered local standard of care). The same test must be used for a subject throughout the study. Clinically significant changes from baseline in LVEF will be reported as AEs.

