Tumor assessments r		X											X s	X				
Survival follow-up															X t			
Additional biomarker blood samples u				X u							X u		X u		X u			

a Last dose of any study drug administered.

b Informed consent for main study (mandatory) and pharmacogenomics (optional).

c Height measured only at Screening.

d These assessments can be performed within 3 days prior to visit.

e Echocardiograms/MUGA scans will be performed at Screening, Cycle 3, at every third subsequent cycle, and End-of-Study Visit. Additional echocardiograms/MUGA scans and electrocardiograms may be performed at the discretion of the investigator. The same test (echocardiogram or MUGA) must be used for a subject throughout the study.

f Collect SAEs only related to the biopsy procedure.

g At 40 days after the last dose of study drug, a telephone call will be placed to the subject to record adverse events.

h PRO assessments will be administered before any study-related procedures are performed.

i Results must be available prior to dosing.

j At Screening, either GFR or the estimated serum creatinine clearance (mL/min) as an estimate of GFR will be calculated. The estimated serum creatinine clearance rate (CrCl; mL/min) will be calculated using the modified Cockcroft-Gault equation ([Appendix 17.1](#)). The estimated GFR will also be calculated before each cisplatin or carboplatin administration. This will be performed only until completion of chemotherapy.

k Intensive serum PK in a subgroup of 30 subjects samples will be collected. See [Table 8.2](#) for detailed information on sampling times.

l See [Table 8.1](#) for detailed information on sampling times.

m Pregnancy test must be confirmed negative before dosing. Additional pregnancy testing may be done at the discretion of the Investigator and/or if required by local regulations for women of child-bearing potential.

n Patritumab administered initially at 18 mg/kg and thereafter 9 mg/kg every 3 weeks as a continuous intravenous infusion over 60 minutes (±10 minutes). Infusion times can be extended to a maximum of 120 minutes for subjects unable to tolerate the 60-minute infusion.

o Cetuximab infusions administered initially at 400 mg/m^2 IV over 2 hours and 250 mg/m^2 over 1 hour weekly. Cetuximab is administered 60 minutes after patritumab administration. Cetuximab is given on Days 1, 8, and 15.

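### The extension phase schedules no LVEF assessment, although maintenance patritumab continues and its dosing rules depend on LVEF (minor)

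*Protocol*

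**What the plan says.** **Extension.** Protocol Section 6.5 places it inside the trial: "Subjects will be provided open-label treatment in an extension phase of this study". It then lists what is done: "the following study procedures will be performed: physical examination, weight, vital signs, hematology, blood chemistry, HAHA levels (and PK) if HAHA is positive", followed by biomarker samples and adverse events. Protocol Table 17.3 and its copy, SAP Table 3.1.2, have no echocardiogram or MUGA row in any column, End of Treatment included. Footnote d of both tables continues patritumab at 9 mg/kg every 3 weeks.

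**LVEF rules.** Protocol Section 5.1.7.1 says "Left ventricular ejection fraction will be monitored throughout the study" and "Dose modification or suspension of patritumab treatment will be based on decreased LVEF, as outlined in Table 5.1". Section 9.11.1 sets the timing: "LVEF will be assessed at Screening, Cycle 3, and then every third subsequent cycle, the End of Treatment Visit", with further scans when clinically called for. In Table 5.1, maintenance patritumab is withheld for "LVEF of less than 40% or LVEF decrease of more than 20% from the baseline", and the condition for restarting is "LVEF of at least 50% (or baseline) based on a repeat echocardiogram or MUGA scan performed in 3 weeks". The same row governs dose reduction and discontinuation.

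**Main-study schedule.** Table 17.2, footnote e, carries the test: "Echocardiograms/MUGA scans will be performed at Screening, Cycle 3, at every third subsequent cycle, and End-of-Study Visit".

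**The concern.** The extension keeps the drug and its dosing rules but schedules no measurement on which the LVEF rule can act. A site following Table 17.3 would do no routine LVEF check on a subject still receiving patritumab. A fall to the withholding level without symptoms gives no clinical prompt for a scan, so it could be missed.

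Sites also need a single answer. Section 6.4 allows no departure from protocol procedures except to remove an immediate hazard. A site that follows Table 17.3 omits scans that Section 9.11.1 appears to require. A site that follows Section 9.11.1 does scans that the extension schedule does not contain. Exposure has no fixed end, because Section 3.1.5 sets no limit on patritumab cycles.

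**Working it through.** **Comparison of the texts**

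| Item | Main study | Extension |
|---|---|---|
| Patritumab maintenance | 9 mg/kg every 3 weeks | 9 mg/kg every 3 weeks |
| Blood count (neutrophil and platelet thresholds, 5.1.7.1) | scheduled | scheduled |
| Chemistry (liver stopping rules, Table 4.1) | scheduled | scheduled |
| LVEF (Table 5.1) | Cycle 3, every third cycle, end of treatment | none |

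Of these dose-gating measurements, only LVEF is absent from the extension. The plan gives no figure for the size of the gap, so there is nothing to reproduce. The estimate below is mine.

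**Inputs.** Median PFS 4.2 and 7.5 months, 12-month enrollment, 1:1 allocation, 10% dropout, and 70 HRG-high plus 35 HRG-low subjects (Protocol 11.10). The patritumab arm is then 35 + 17.5 = 52.5. Closure is 13 months after the last randomization, 25 months in all (3.1.4). Cycles last 21 days (3.1.5), so the scan interval is 3 × 21 = 63 days. One month is 30.4 days (SAP 8.2.1). I assume exponential PFS and uniform enrollment.

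**Progression-free at closure.** With L = ln 2 / median, the expected fraction is (exp(−13L) − exp(−25L)) / (12L).
- Median 4.2: 0.0509
- Median 7.5: 0.1817

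Expected patritumab-arm subjects, with the value after 10% dropout (× 0.9) in parentheses:
- No treatment effect: 52.5 × 0.0509 = 2.67 (2.41)
- Effect in HRG-high only: 35 × 0.1817 + 17.5 × 0.0509 = 6.36 + 0.89 = 7.25 (6.53)
- Effect in both strata: 52.5 × 0.1817 = 9.54 (8.59)

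**Nine-weekly scans per subject before progression.** T = 63 / 30.4 = 2.07 months.
- If the 63-day clock restarts at closure, the expectation is 1/(exp(LT) − 1): 2.45 (median 4.2) and 4.74 (median 7.5).
- If the clock runs on from Cycle 3, as Section 9.11.1 implies, and subjects reach closure at a uniformly spread point in the interval, it is 1/(LT): 2.92 and 5.22.

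**Total scans**

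| Scenario | Clock restarts, after dropout | Clock restarts, no dropout | Clock runs on, after dropout | Clock runs on, no dropout |
|---|---|---|---|---|
| No effect | 6 | 7 | 7 | 8 |
| HRG-high only | 29 | 32 | 32 | 36 |
| Both strata | 41 | 45 | 45 | 50 |

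The lowest entry is 0.9 × 2.67 × 2.45 = 5.9. The highest is 9.54 × 5.22 = 49.8. End of Treatment adds one scan per subject.

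**Checks already made by closure, with no dose delays.** The last subject randomized has 13 × 30.4 = 395 days, or 18.8 cycles, so scans at Cycles 3 to 18: 6. The first has 25 × 30.4 = 760 days, or 36.2 cycles, so scans at Cycles 3 to 36: 12.

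**SAP text.** SAP Section 5.2.6 places LVEF at screening and end of study treatment and leaves the rest to the investigator. That departs from Protocol 9.11.1 and from the SAP's own Table 3.1.1, footnote e.

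**The case against.** The best reply is that the specific text governs. Section 6.5 gives its own list for the period after main-study closure and points to its own table. Section 9.11.1 is anchored to Screening and Cycle 3, and the visits that implement it belong to the main-study treatment period. Table 17.3 also drops ECOG, although Section 10.1 asks for it at every scheduled visit, along with the ECG, urinalysis, pregnancy test, patient-reported outcomes, concomitant medications and tumor assessments. That looks like a deliberately reduced schedule.

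This stands as a reason for moderate rather than high confidence. It does not settle the matter. No sentence suspends Section 5.1.7.1 or Table 5.1, and patritumab dosing does not depend on the dropped ECOG and patient-reported outcomes as it does on LVEF. The extension texts also disagree with each other: Section 6.5 lists weight, while Table 17.3 has no weight row. Oversight is therefore at least as plausible as intent.

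Two stronger readings are tempting. A reader might infer that Table 5.1 is disabled in the extension. It is not: Section 9.11.1 allows clinically indicated scans, Table 17.2 footnote e allows discretionary ones, and examinations, vital signs and adverse-event collection continue. What is missing is the routine scan. A reader might also infer a known cardiac hazard. Sections 1.1.1.5 and 1.3 name no cardiac reaction to patritumab, and subjects dosed without delay would already have had 6 to 12 on-treatment checks.

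**Conclusion.** The inconsistency is real and minor. Patritumab and the LVEF dosing rule carry into the extension, the scheduled measurement does not, and the documents do not say that this is intended. PFS and OS are unaffected.

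About 3 to 10 patritumab-arm subjects would be expected to be progression-free at closure, and roughly 6 to 50 nine-weekly scans would go unscheduled in total, plus one per subject at End of Treatment. The range reflects treatment effect, dropout and scan timing. It rests on exponential PFS at the planning medians, uniform enrollment and closure at 25 months.

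A reader might take these figures as ceilings. They are expected values: chance, or PFS longer than planned, could raise them. Optional entry, earlier drug discontinuation or later closure would lower them. A reader might also add control subjects. Section 6.5 speaks of continuing study treatment and does not describe placebo subjects starting patritumab, so none are counted.

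**What to change.** For subjects receiving patritumab, add an echocardiogram or MUGA scan every third cycle and at End of Treatment to the Section 6.5 list and to Table 17.3. Copy the row into SAP Table 3.1.2 and bring SAP Section 5.2.6 into line with Protocol Section 9.11.1. If the omission was deliberate, a sentence exempting the extension and stating how Table 5.1 then applies would also remove the conflict.

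The cost is one phrase and one table row in a protocol amendment, two small SAP edits, and the scans estimated above. The test is one that Section 9.11.1 already requires, so no new procedure is introduced.

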## 7. EFFICACY ASSESSMENTS

Tumor response assessments, including subjects who discontinued from treatment, will be performed every 6 weeks ( $\pm$  3 days) for the first 24 weeks independent of treatment cycle until disease progression, death, start of new anticancer therapy, withdrawal of subject consent, lost to follow-up, or study closure, whichever occurs first. After 24 weeks, tumor assessments will be performed every 12 weeks ( $\pm$  7 days).

### 7.1. Primary Efficacy Variable

The primary efficacy variable is PFS. This is defined as the time from the date of randomization to the earlier of the dates of the first objective documentation of radiographic disease progression (per RECIST v1.1 as assessed by investigator-see [Appendix 17.3](#)) or death due to any cause. Progressive Disease is defined as  $\geq$  20% increase in the sum of diameters of target lesions; taking as reference the smallest sum on study (this includes the baseline sum if that is the smallest on study). In addition to the relative increase of 20%, the sum must also demonstrate an absolute increase of at least 5 mm. (Note: the appearance of one or more new lesions is also considered progression).

Subjects with a global deterioration of health status requiring discontinuation of treatment without objective evidence of disease progression at that time should be reported as “clinical progression.” Every effort should be made to document objective progression even after discontinuation of treatment. Symptomatic deterioration is not a descriptor of an objective response: it is a reason for stopping study therapy. The objective response status of such subjects is to be determined by evaluation of target and non-target disease. If a radiographic tumor assessment has not been performed within 4 weeks of the time of clinical progression, then another radiographic assessment should be performed without waiting for the next regularly scheduled scan.

For equivocal findings of progression (ie, very small and uncertain new lesions, cystic changes, or necrosis in existing lesions), treatment may continue until the next scheduled assessment. If at the next scheduled assessment, progression is confirmed, the date of progression should be the earlier date when progression was suspected.

### 7.2. Secondary Efficacy Variable(s)

- Overall survival and objective response rate

### 7.3. Exploratory Efficacy Variable(s)

- Duration of response, time to response, time to disease progression, duration of SD

## 8. PHARMACOKINETIC/PHARMACODYNAMIC ASSESSMENTS

### 8.1. Pharmacokinetic (PK) Variable(s)

All subjects will have a PK sample for serum patritumab collected at Cycles 1- 3 and at End of Study Treatment Visit as shown in Table 8.1. This will be a sparse PK assessment (limited sampling).

**Table 8.1: Sparse PK Assessments (Patritumab Only) for All Subjects**

Cycle 1		Cycle 2		Cycle 3		End of Treatment
Pre-inf (collected with HAHA sample)	EOI	Pre-inf (collected with HAHA sample)		Pre-inf (collected with HAHA sample)	EOI	Collected with HAHA sample

Pre-inf = Preinfusion, EOI = end of infusion, HAHA = human antihuman antibody. EOI samples should be collected  $\pm$  10 min of the end of patritumab infusion.

For a subset of 30 subjects, a blood sample for PK analyses of patritumab, cetuximab, and platinum concentrations will be obtained at the time points, relative to the start of patritumab infusion at Cycle 1, shown in Table 8.2. This will be an intense PK assessment.

**Table 8.2: Sub Study: Intensive PK Assessments Relative to the Start of Patritumab Infusion at Cycle 1 [n = 30]**

Study Treatment	Pre-inf	Day 1						Day 2	Day 3	Day 8	Day 15	Day 21
		1 h (EOI) $\pm$ 10 min	3 h $\pm$ 10 min	4 h $\pm$ 10 min	5 h $\pm$ 10 min	6 h $\pm$ 10 min	7 h $\pm$ 10 min	24 h $\pm$ 1 h	48 h $\pm$ 1 h	168 h $\pm$ 24 h	336 h $\pm$ 24 h	504 h $\pm$ 24 h
Patritumab	X	X	X	X	X	X	X	X	X	X	X	X
Cetuximab	X		EOI	X	X	X	X	X	X	X		
Cisplatin	X				EOI	X	X	X	X			
or												
Carboplatin	X			4.5 h EOI	X	X	X	X	X			

Pre-inf = Preinfusion, EOI = End of infusion, h = hours, min = minutes.

Note: One blood sample to produce 3 mL of serum sample will be collected at each time point. The resulting serum will be divided into 3 aliquots of 1 mL for analysis of each analyte depending on the dose regimen. Further details will be provided in the lab manual.

Patritumab will be infused over 1 hour followed by cetuximab infused over 2 hours (end of infusion at  $\sim$ 3 h) and then a 1 h pause ( $\sim$ 4 h). Then cisplatin will be infused over 1 hour (end of infusion  $\sim$ 5 h) or carboplatin infused over 30-60 minutes (end of infusion  $\sim$ 4.5 h). Subjects will remain in the clinic for hydration following cisplatin/carboplatin

infusions for approximately 2 hours following infusions to complete hydration (ie, ~7 h in total). Only one blood sample will be collected at each scheduled time point and the resulting serum will be aliquoted for each analyte. Blood collection should approximately correspond to EOI of each drug as listed, at the nominal times defined relative to the start of patritumab infusion.

Serum concentrations of patritumab, cetuximab, and platinum will be measured, as appropriate, using validated assays. Specific instructions for collection and shipping of PK samples will be provided in the Laboratory Manual.

## **8.2. Pharmacodynamic Variable(s)**

Not applicable.

## **8.3. Predictive Biomarker and Exploratory Variable(s)**

A predictive biomarker will be analyzed with the intent of identifying those subjects who might derive clinical benefit from treatment with patritumab. Heregulin is the candidate biomarker prospectively selected as the single predictive biomarker. Heregulin messenger RNA will be measured in tumor samples using a quantitative reverse transcription polymerase chain reaction assay.

Subjects with HPV positive status will be included. Molecular and epidemiological studies strongly suggest HPV-positive oropharyngeal cancers comprise a distinct molecular, clinical, and pathologic disease entity that is likely associated with HPV infection and for which SCCHN patients who are HPV positive have a markedly improved prognosis. In addition, it has been shown that other SCCHN subtypes have been found to be p16 positive such as nasopharyngeal, hypopharyngeal, laryngeal, and in the oral cavity. Therefore, HPV status or p16 will be evaluated in all tumor tissue in this study.

Further exploratory tissue, soluble, or genomic biomarkers in subject tissue and blood samples (possibly including circulating cell-free DNA and exosomes) may be analyzed based on emerging scientific knowledge to better understand the target disease and also the effects of study treatment.

For instructions on management of blood and tissue samples please refer to the laboratory manual.

